3.0 Introduction

Ankylosing spondylitis (AS) and psoriatic arthritis (PsA) are the major subtypes of rheumatic diseases named as spondyloarthritides (SpAs). The most important clinical features of this group are inflammatory back pain, asymmetric peripheral oligoarthritis, predominantly of the lower limbs, enthesitis and specific organ involvement such as anterior uveitis and chronic inflammatory bowel disease.

3.1. Ankylosing spondylitis

Ankylosing spondylitis (AS) is the prototype of SpAs and primarily affects the axial skeleton, with a characteristic involvement of the spine and sacroiliac joints, synovitis of peripheral joints may occur as well. Pain, stiffness due to inflammation and progressive spinal ankylosis that may lead to complete spine rigidity (total spinal ankylosis) are the clinical hallmarks of the disease. Inflammation may also affect entheses, heart, lung, intestine and eyes. The prevalence of AS appears to be substantially higher than previously estimated, approximating 0.9% in Caucasians (1). This resembles the prevalence of rheumatoid arthritis (RA), but unlike RA, AS is more common in men than in women. The average age at onset of AS is in the third decade, which can necessitate treatment for several decades. In addition, due to the early onset, development of functional disability and life-time costs, the socioeconomic impairment for subjects with active AS is likely to be high. Recent surveys have shown that AS is associated with a comparable disability to that observed in RA with substantial direct and indirect costs (2).

Work disability in AS and its costs

Due to its early onset, chronicity and consequent functional impairment, AS carries a significant economic burden, arising from both the direct costs of medical and disability care and from indirect costs associated with loss of earnings and decreased productivity. The prevalence of work disability in AS patients was found to range from 13 - 46% (3-7).

A Dutch study reported a significant 11%-reduction in overall participation in the labor force, compared with the age matched general population. More than 75% of patients with AS who had stopped working were officially recognized as work disabled (8). The withdrawal rates from work in patients with AS were reported to be about 3-times higher than in the general population (9). Data from a Swedish Registry showed that AS patients have an increased risk of sick leave, with a relative risk of 1.8 and median of 30 additional sick days per year compared with population-based controls (10). A UK-based study suggested that 50% of AS patients at working age lost their job due to AS activity, and of those in work 50% were work unstable, at moderate or high risk of job retention problems (11). The society costs of lost productivity due to AS were estimated at 3.595 EUR per patient per year (12).

Treatment of AS

Nonsteroidal anti-inflammatory drugs (NSAIDs) and physical modalities are the current standard therapy for AS. Evidence exists that NSAIDs treat the symptoms of AS, but it has not been confirmed that NSAID therapy reliably influences spinal mobility, acute phase reactants (e.g., ESR and CRP) or the long-term disease course with respect to the development of ankylosis (13, 14).

The advent of tumour necrosis factor α (TNF- α) blockade marks the first major therapeutic advance in AS since the introduction of NSAIDs. Treatment with anti-TNF- α agents has been proven to provide significant improvements in clinical symptoms, physical function and patients' health related quality of life (15).

Of the available TNF- α antagonists, adalimumab is the first fully human monoclonal antibody that binds with a high affinity to both free serum and membrane bound TNF- α . Adalimumab therapy has been proven to effectively and long-term reduce the signs and symptoms of AS (16, 17), including in patients with total spinal ankylosis (18), and extra-articular manifestations, such as uveitis (19). Treatment with adalimumab also significantly improved physical health status and quality of life (20). A recent post-hoc

analysis of ATLAS trial (16), which was basically aimed at assessing the factors associated with work ability and disability in patients with AS, also demonstrated that adalimumab sustains improvements in work outcomes, as measured by Work Productivity and Activity Impairment – Specific Health Problem Questionnaire (WPAI-SHP) (21). Due to the study design, however, these findings did not allow for a definite conclusion that the improvements in work outcomes were a direct result of adalimumab therapy (21).

3.2. Psoriatic arthritis

Psoriatic Arthritis (PsA) is an inflammatory arthropathy that occurs in up to one third of patients with psoriasis and is usually diagnosed years after the appearance of psoriatic skin disease, but may also precede it.

Synovitis of peripheral joints is a major feature of PsA, and joint affection can be monoarthritic, oligoarthritic, or polyarthritic. More than half of patients with PsA exhibit progressive, erosive arthritis that often is associated with functional impairment. PsA may also affect the axial skeleton: the spine can be involved in any part, most often at the lumbosacral transition and the neck.

PsA can develop at any time, but for most people it appears between the ages of 30 and 50, and it affects men and women equally. The overall prevalence of PsA is approximately 0.1% (22, 23).

Work disability in PsA and its costs

There is a dearth of published pharmacoeconomic studies in PsA, despite increasing evidence that affected patients can have significant radiographic joint damage, functional impairment, reduced quality of life (QoL) and long-term work disability. Among patients treated with anti-TNF agents and registered in the British Society for Rheumatology Biologic Register, work disability rates were 39% for PsA patients, 41% for AS patients and 49% for those with RA (24). Somewhat lower rates were reported for Norwegian PsA

patients on either conventional or biologic DMARD (disease modifying anti-rheumatic drugs) therapy: work disabled were 32.7% of females and 17.4% of males (25).

Treatment of PsA

The treatment of PsA is directed at controlling the inflammatory process. Although there is no clear correlation between the skin and joint inflammation in every patient, the skin and joint aspects of the disease need to be treated simultaneously. Initial treatment consists of NSAIDs for joint disease and topical or systemic therapy for the skin. More severe disease is likely to require treatment with DMARDs, such as MTX, and intra articular steroids. Among second-line treatments used in RA and evaluated in patients with PsA are sulfasalazine, MTX, leflunomide, gold, antimalarials, cyclosporine, and azathioprine (26).

Anti-TNF agents are highly effective in treating the signs and symptoms of PsA, including dactylitis and enthesitis, and they also suppress structural joint damage and treat skin psoriasis (27).

Treatment with adalimumab, dosed at 40 mg s.c. every other week, showed in placebo controlled clinical trials ACR20 response rates of 39-58% and ACR50 response rates of 25-39% in patients with active PsA who had failed previous standard therapy (45, 46). Significant improvements of psoriatic skin changes and disease-related quality of life were also noted (28).

Data on the impact of biologic therapy on work disability and productivity in patients with PsA are scarce. A study that determined the cost-effectiveness of anti-TNF treatment in patients with RA, PsA and AS in a real-world setting found that the number needed to treat (NNT) in order to achieve the minimal clinically important difference in HAQ score (decrease by ≥ 0.2) was about 2 for all three evaluated diseases: 1.94 for RA, 1.88 for PsA and 2.30 for AS (29). After 14 weeks of treatment with infliximab, median productivity as measured on a 0 to 10 visual analog scale improved significantly compared with the placebo group (30). Results of the recently published ACCLAIM study in patients with

PsA on adalimumab therapy demonstrated significant improvements (decreases) from baseline to week 12 in 3 of the 4 domains assessed by the Work Limitations Questionnaire (WLQ): Physical, Time and Output (31).

4.0 Rationale

Ankylosing spondylitis (AS) and psoriatic arthritis (PsA) are both associated with often debilitating clinical symptoms, reduced functional impairment and significant impact on quality of life. As a consequence both diseases imply a significant economic burden, arising from both the direct costs of medical and disability. Health economics data becomes increasingly important to justify the costs of medicines.

Very limited data are available about the employment status and the work productivity of patients with AS and PsA in Belgium. The same is true for the impact of adalimumab treatment on employment status and work productivity.

The aim of this study is to analyse the employment status and work productivity of patients with AS and PsA before and after the start of adalimumab and to look at the relationship between employment status, work productivity, disease activity and clinical evaluations.

5.0 Study Objectives

5.1 Primary Objective

The main objective of the study is to observe in daily practice the evolution of work productivity over 18 months in AS and PsA patients after the start of adalimumab treatment.

The following questions will be addressed:

- What is the employment status of AS and PsA patients with active disease before initiation of adalimumab?
- In the patients who work at baseline, what is their work productivity?
- Does adalimumab therapy enable people with AS and PsA to return to work or work more productively?

5.2 Secondary Objectives

- Investigate if there is a difference in evolution of employment status and work productivity after initiation of adalimumab treatment between AS and PsA patients throughout the study
- Investigate the relationship between disease activity and employment situation and the relationship between clinical evaluations and employment situation at baseline and after 18 months
- Investigate possible correlations between disease activity and work productivity and between clinical evaluations and work productivity

5.3 Primary endpoints:

Total work productivity impairment (TWPI) due to AS/PsA :18 months versus baseline in all patients, measured by the WPAI-SHP questionnaire. (Patient reported outcome)

5.4 Secondary endpoints:

- Total work productivity impairment (TWPI) due to AS and PsA separately: 18 months versus baseline in all patients, measured by WPAI-SHP questionnaire. (Patient reported outcome)
- Evolution over time of (observed for AS and PsA combined and separately) :
 - Number of patients that are employed at each assessed visit

- Percentage of missed working hours (absenteeism) due to As/PsA 7 days prior to each visit
- Assessment of the effect of As/PsA on the ability to do regular daily activities during the 7 days prior to each visit (activity impairment)
- Assessment of the effect of As/PsA on productivity while working during the 7 days prior to each visit (presenteeism)
- Health Related Quality of Life (Patient reported outcome)
 - HAQ-DI (PsA)
 - DLQI (PsA)
 - HAQ-S (AS)
- Disease activity measures and clinical evaluations:
 - DAS28 (PsA)
 - BSA (PsA)
 - BASDAI (AS)
 - Acute phase reactants (CRP / ESR)
 - Physician assessment of disease activity (VAS)
 - Patient assessment of disease activity (VAS)
 - Patient assessment of pain (VAS)

6.0 Investigational Plan

6.1 Selection of Study Population

The study population will consist of adult patients with diagnosed AS / PSA in whom adalimumab treatment will be initiated. All medications will be prescribed in the usual manner in accordance with the terms of the marketing authorization and in line with the Belgian reimbursement criteria.

The patients must provide written informed consent prior to study participation and must give written authorization to the investigator to use and/or disclose personal and/or health data before entry into this observational study.

6.1.1 Inclusion Criteria

- Patients ≥ 18 years and ≤ 50 years
- Diagnosed with AS or PsA
- Patient newly initiated on adalimumab (according to the Marketing Authorization and Belgian reimbursement criteria)
- Signed Informed Consent

6.1.2 Exclusion Criteria

- Any contraindication for adalimumab as specified in the corresponding SmPC
- Patients previously treated with biologics
- Patients participating in other AbbVie-sponsored trials

6.2 Number of Patients to be Enrolled

It is anticipated to enroll 200 patients in the study. Patients will be enrolled by approximately 25 centers in Belgium. Each centre will include on average 8 patients during the 12 month recruitment period.

6.3 Investigator Selection Criteria

Approximately 20 centers across Belgium will be asked to participate in this study. Centers can be University hospitals, regional hospitals, private practices.

Following criteria will be used when selecting investigators:

- Experience and interest to participate in observational studies
- Experience in AS / PsA patient care

- Sufficient patient potential to include the required number of patients in the study
- Required availability and resources to participate in this observation study
- Acceptance of study protocol and study procedures

6.4 Study Duration

Data will be collected during routine visits at baseline and afterwards preferably after 3, 6, 12 and 18 months. The total duration of the observation period for the study will therefore be approximately 18 months.

Patients can be withdrawn from the study at any time during the study when the patient withdraws his/her consent or if the investigator finds it no longer appropriate to keep patients in the study.

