APPENDIX G: Study Plan

	Screening	Baseline	Month 3	Month 6	Month 12	Month 18 (or term.)
Informed Consent	♦					
Inclusion/ Exclusion Criteria	♦					
Medical History		♦				
Demographics (gender, year of birth, race)		♦				
AS & PSA diagnosis		♦				
Previous and current AS&PsA treatments		♦				
Extra articular disease manifestations		♦	♦	♦	♦	♦
Educational background		♦				
Employment situation		♦	♦	♦	♦	♦
Disease activity measures and clinical evaluations : DAS28*, BSA*, physician assessment disease activity, acute phase reactants (CRP/ESR), BASDAI**, patient assessment of disease activity, patient assessment of pain						
		♦	♦	♦	♦	♦
Healt related quality of life (DLQI*, HAQ-DI*, HAQ-S**)		♦	♦	♦	♦	♦
WPAI-SHP		♦	♦	♦	♦	♦
Serious Adverse Events		♦	♦	♦	♦	♦

Screening and basline assessments can happen in the same visit

Follow up visits are according to daily clinicla practice, no additional visits are planned for the study only.

*only completed for PsA patients

** only completed for AS patients

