1.3 Study Design

The study population consists of adult patients between 18 and 50 years of age, with diagnosed AS / PsA in whom adalimumab treatment was initiated. All medications were prescribed in the usual manner in accordance with the terms of the marketing authorization and in line with the Belgian reimbursement criteria.

The patients provided written informed consent and gave written authorization to the investigator to use and/or disclose personal and/or health data before entry into this observational study.

200 patients were to be enrolled in 20 investigational sites in Belgium during a recruitment period of 12 months. Centers could be University hospitals, regional hospitals, or private practices, with Experience in AS / PsA patient care. Other criteria to be used when selecting investigators were experience and interest to participate in observational studies, sufficient patient potential to include the required number of patients, required availability and resources to participate, and acceptance of the study protocol and study procedures.

Patient data were collected during routine visits at baseline and afterwards preferentially after 3, 6, 12, and 18 months. The total duration of the observation period for the study was therefore approximately 18 months.

This is a local, post marketing, observational study (PMOS). As this is an observational study, no additional visits were required, no study specific medication was provided and no other interventional procedures additional to those comprising routine clinical practice were performed.

All of the following criteria were to be fulfilled to make the patient eligible for the study:

- Inclusion criteria:
 - Age \geq 18 and \leq 50 years
 - Patient diagnosed with AS or PsA
 - Patient newly initiated on adalimumab (according to the Marketing Authorization and Belgian reimbursement criteria)
 - Patient has signed the Informed Consent Form.
- Exclusion criteria:
 - Patients having any of the contraindications mentioned in the SmPC
 - Patients previously treated with biologics
 - Patients participating in other AbbVie-sponsored trials.

A patient was withdrawn from the study if he/she withdrew consent or if the investigator found it no longer appropriate to keep the patient in the study.

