Study termination

- Study completion or study withdrawal date.
- Reason for study termination:
 - Study completion
 - Withdrawal of consent.
 - Lost to follow-up.
 - Discontinued due to administrative reasons.
 - Death.
 - Serious adverse event.
 - Discontinued due to other reason.

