1.6 Derived Variables

- Age (years) = year of inclusion – year of birth
- Study duration (month) =
$$12 \times (\text{date patient completed study/withdrew} - \text{date of inclusion}) / 365.25$$
- Adalimumab treatment duration (month) =
$$12 \times [\text{first of (last stop date adalimumab and date patient completed study/withdrew)} - \text{start date adalimumab} + 14] / 365.25$$
- BASDAI total score = [(Item 1+Item 2+Item 3+Item 4)+(Item 5+Item 6)/2]/5:
If one of items 5 or 6 is missing the other is considered.
If one of items 1, 2, 3, 4, or the average of 5 and 6 is missing, the missing item is estimated by the average of the available among items 1, 2, 3, 4, and the average of items 5 and 6. If more than one of these is missing, the total score is missing.
- BASDAI category (axial disease):
 - Yes: BASDAI total score >4
 - No: BASDAI total score ≤ 4 .
- HAQ-DI
Each of the 8 categories is given a score by taking the maximum score of all questions in the category (question in each category with the highest score is the score for that category).
The HAQ-DI will be calculated by dividing the sum of the category scores by the number of categories with at least 1 question answered. If fewer than 6 categories have responses, no disability score will be calculated. The HAQ-DI score ranges from 0 to 3. A lower HAQ-DI disability score indicates better function.
- HAQ-S
Each of the 10 category is given a score by taking the maximum score of all questions in the category (question in each category with the highest score is the score for that category). If the maximum score equals 0 or 1, but a device related to that category is used, or help from another person is provided for the category, then the category score is increased to 2. If the category score is already 2, and a device related to that category is used, or help from another person is provided for the category, the score for that category remains 2. The table below details how each aid and device is associated with the category scores.

If all questions within a given category are unanswered, no score will be provided for that category. The HAQ-S will be calculated by dividing the sum of the category scores by the number of categories with at least 1 question answered. If fewer than 6 categories have responses, no disability score will be calculated. The HAQ-S score ranges from 0 to 3. A lower HAQ-S disability score indicates better function.

NOTES:

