1.9 Data Handling

The following data handling transformations are performed for the analysis:

Onset data

- Date of enrolment is taken to be date of informed consent

WPAI Questionnaire

- For patients with (number of hours missed due to psoriasis = number of hours worked = 0), Absenteeism, Presenteeism and Total work productivity impairment are set to missing.
- If the answer to Question 1 of the WPAI Questionnaire is not YES but there is an answer to any of Questions 2, 3, 4, or 5, then the answers to these questions are considered to be missing.

Serious Adverse Events

In case of a partial or missing date for the start of a serious adverse event it will be

assumed that the event was study-emergent unless it can be determined from the partial start or stop date that the event definitely started before the date of informed consent or more than 70 days after the last administration of study medication.

Last Observation and Last Attended Visit

The analysis of individual scales is performed for each visit and for the last observation after baseline. For multi-item questionnaires the last observation after baseline is defined as the observation for the last visit after baseline at which any of the items of the questionnaire is completed.

The analysis of the relation between variables is performed for data recorded at baseline, at Month 18, and at the last attended visit.

Other Missing Data

No other estimation will be performed of missing data. In order to obtain estimates for the end of the study, use is made of the last observation after baseline. If date of completion/withdrawal was missing it has been set to date of last contact.

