1.10 Changes from the Analysis Foreseen in the Protocol

For the DLQI the protocol only foresaw an analysis of the total score and the categories. In order to provide additional information descriptions will also be provided for the 6 scales of the DLQI, and for the regrouped categories ≤ 5 and > 5 .

The protocol foresaw to analyse the evolution of the work productivity data, the health-related quality of life scores, and the disease activity measures and clinical evaluations based upon the data collected in time windows around the foreseen study visits. Since data were collected in the CRF around the planned visits, it was decided to analyse the data by reported study visit.

Since an important proportion of patients dropped out before the Month 18 visit it was decided also to perform analyses for the last observation after baseline.

The protocol did not foresee to perform an analysis of the safety data. It was decided to perform an analysis of adverse events and of the course of the study and for this purpose a safety analysis set was defined.

In order to better comprehend the effect of employment status it was decided to provide frequencies of extra-articular disease manifestations broken down by employment status.

The protocol foresaw to primarily perform the analysis on the basis of the PPS and to perform a sensitivity analysis of the TWPI on the ITT Set. It was decided only to perform the latter analysis in case the difference between the two analysis sets exceeds 10% of the patients of the PPS.

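### Observation can be ended at the investigator's discretion with no follow-up afterwards, so the Month 18 TWPI may be missing in relation to outcome

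*Protocol*

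**What the plan says.** **Withdrawal.** Besides withdrawn consent, Protocol 6.4 allows withdrawal at any time "if the investigator finds it no longer appropriate to keep patients in the study". SAP 1.3 has the same rule: "if the investigator found it no longer appropriate to keep the patient in the study". Neither gives criteria.

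**Termination reasons.** SAP 1.5 lists study completion, withdrawal of consent, loss to follow-up, administrative reasons, death, "Serious adverse event" and "Discontinued due to other reason". Lack of effect, a non-serious adverse event and a switch of drug have no code. No specification field is shown for the last item, although other SAP 1.5 items have one.

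**Treatment and observation are separate.** Protocol 6.5 says that no study medication is supplied and no extra visits are required. The treatment-duration formula in SAP 1.6 takes the earlier of "last stop date adalimumab and date patient completed study/withdrew", so a patient can stop adalimumab and stay under observation. SAP 1.5 records adalimumab dates, but no reason for stopping.

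**Dropout and its handling.** SAP 1.10 adds analyses of the last observation after baseline, with this reason: "Since an important proportion of patients dropped out before the Month 18 visit". SAP 1.9 then states: "No other estimation will be performed of missing data". Protocol Appendix G schedules the WPAI-SHP in a final column headed "Month 18 (or term" (short for termination).

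**The concern.** The primary endpoint is the TWPI change from baseline to Month 18 in all patients. In a study that only observes routine care, a WPAI completed at a routine visit is as informative after adalimumab has been stopped or changed as before. A withdrawal rule without criteria can remove such patients from observation, and an SAE is a recorded way out. Nothing asks for the questionnaire afterwards.

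If those who leave have fared worse at work than those who stay, the Month 18 mean describes the stayers and flatters the change among all who started. The planned 95% confidence interval covers sampling error only and would give no sign of this. The planned outputs tabulate termination reasons (SAP 4) but do not show TWPI by reason or by completer status, so a reader could not judge how far the loss was related to outcome.

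**Working it through.** **1. The plan's precision figures.** From Protocol 10.1 and SAP 1.4: 200 enrolled, 65% working, 80% of those with 18-month data, SD of the change 23.8 (alternative 30.0).

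- Employed at baseline: 200 x 0.65 = 130.
- Evaluable: 130 x 0.80 = 104, which the plan rounds to about 100.
- Half-width = t(0.975, n-1) x SD / sqrt(n). At n = 100 this is 4.72 for SD 23.8 and 5.95 for SD 30.0. All six published intervals are reproduced to one decimal.

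**2. Bias of the completers' mean.** Let c be the completers' mean change, m the mean change that leavers would have shown at Month 18, and d the share missing. The mean in all starters is (1-d)c + dm, so the bias is c - [(1-d)c + dm] = d(c - m).

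Take c = -15, the middle value in the plan's table. The value d = 20% is the plan's own; 30% and 40% are assumptions, as is every m. With n = 130(1-d):

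| d | n | m = -15 | m = -10 | m = -5 | m = 0 | m = +10 | Half-width, SD 23.8 | Half-width, SD 30.0 |
|---|---|---|---|---|---|---|---|---|
| 20% | 104 | 0 | -1.0 | -2.0 | -3.0 | -5.0 | 4.63 | 5.83 |
| 30% | 91 | 0 | -1.5 | -3.0 | -4.5 | -7.5 | 4.96 | 6.25 |
| 40% | 78 | 0 | -2.0 | -4.0 | -6.0 | -10.0 | 5.37 | 6.76 |

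For example, at d = 20% and m = 0 the mean in all starters is 0.8 x (-15) + 0.2 x 0 = -12.0, against -15.0 observed. At d = 30% it is 0.7 x (-15) = -10.5. A negative bias overstates improvement. The sign reverses if leavers improved more than completers: m = -20 at d = 20% gives 0.2 x (-15 + 20) = +1.0.

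**3. What the safeguards supply.** The termination WPAI and the last-observation analysis (SAP 1.9, 1.10, 5.1) retain a value for patients who leave after some follow-up. That value belongs to the time of leaving, and later change in either direction is not seen. Patients with no follow-up data are excluded from the ITT, Per Protocol and Safety Sets alike (SAP 1.8), so last observation cannot include them.

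**The case against.** A reader might infer that Month 18 data are in fact lost selectively in patients who do badly, or that sites will use the rule to remove those who stop adalimumab. The documents support neither. SAP 1.10 gives no size, reason or direction for the dropout. An SAE is listed as a recorded reason for termination, not as an instruction to withdraw, and it is not the same as poor work productivity. The SAP 1.6 formula shows that stopping the drug does not by itself end observation.

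A reader might also infer that outcome-related exits cannot be told from neutral ones. That goes too far. Loss to follow-up, administrative reasons, consent withdrawal and death have their own codes. Adalimumab dates, other AS/PsA drugs with dates, and the action taken after an SAE are recorded, and SAP 6.2 tabulates non-serious events that cause treatment discontinuation. Many switches and event-related stops can be traced from these. The gap is narrower: no code for lack of effect, no reason attached to the stop date, and no display of TWPI by exit.

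The size also needs care. The plan's 20% covers all employed patients without 18-month data, not only investigator withdrawals. It can include missed routine visits and patients no longer working, for whom TWPI is undefined whatever the withdrawal rule says. The study is declared descriptive, and the SAP describes conduct in the past tense, so new protocol wording may come too late for this cohort.

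These objections reduce the point to a risk. They do not remove it: the rule has no criteria, no later WPAI is required, and last observation is the only handling of the loss.

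**Conclusion.** The point holds as a risk of outcome-related missingness in the primary variable, not as a demonstrated bias. With completers at -15 and leavers at 0 (assumed), improvement is overstated by 3.0 points at the plan's 20% loss. That lies within the 4.6-point half-width at n = 104 and SD 23.8. At an assumed 30% loss it is 4.5 points against 5.0 (n = 91). At an assumed 40% it is 6.0 points, above the 5.4-point half-width for SD 23.8 but below 6.8 for SD 30.0. If leavers resemble completers, the bias is zero. The planned outputs would not let a reader tell these cases apart, and a change in collection and reporting is worth making.

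**What to change.** **Data collection.** State in Protocol 6.4 and SAP 1.3 that stopping or changing adalimumab, or an SAE, does not by itself end data collection. The WPAI and employment items should continue at routine visits to Month 18 unless consent is withdrawn, the patient dies or is lost to follow-up. This concerns data collection only and makes no statement about treatment. Add a coded reason (lack of effect, adverse event, switch, other) to the adalimumab stop date already recorded.

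**Data already collected.** Show baseline and last TWPI by completer status and by recorded termination reason. Use the adalimumab, concomitant-drug and adverse-event records to classify exits where possible; no free text behind the other-reason code should be assumed.

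**Analysis.** Add to SAP 5.1 one sensitivity analysis of the Month 18 TWPI change beyond last observation. A mixed model using all visits would serve if missingness depends on observed values; a delta adjustment for leavers would show how far departures from that matter.

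**Cost.** Some protocol and SAP wording, one CRF field and a few tables; the visits take place anyway. The downside is small: some follow-up will reflect other treatments, and TWPI stays undefined for patients no longer working, so they must be reported through the employment endpoint.
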